FDA	Food and Drug Administration
GAIS	Global Aesthetic Improvement Scale
HA	Hyaluronic Acid
ICH	International Conference on Harmonization
IDE	Investigational Device Exemption

Abbreviation	Definition
[REDACTED]	[REDACTED]
ITT	Intent-to-Treat population
LTFU	lost-to-follow-up
MedDRA	Medical Dictionary for Regulatory Activities
[REDACTED]	[REDACTED]
[REDACTED]	[REDACTED]
PP	Per Protocol population
PSAQ	Periorbital Subject Assessment Questionnaire
PT	Preferred Term
[REDACTED]	[REDACTED]
SAFT	Safety population
SAP	Statistical Analysis Plan
SAS	Statistical Analysis Software
SD	Standard Deviation
SOC	System Organ Class
TI	Treating Investigator
TIOHS	Teoxane Infraorbital Hollows Scale
[REDACTED]	[REDACTED]
UPT	Urine Pregnancy Test

Abbreviation	Definition
US	United States
[REDACTED]	[REDACTED]
WHO-DD	world health organization drug dictionary

1. Introduction

This statistical analysis plan (SAP) describes the planned analysis and reporting for [REDACTED] [REDACTED] protocol/clinical investigation plan (CIP) [REDACTED] (A Randomized, Blinded Evaluator, No-treatment Control, Multicenter, Prospective Clinical Study of RHA [REDACTED] for the Treatment of Moderate to Severe Tissue Volume Deficiencies in the Infraorbital Regions), [REDACTED] [REDACTED]. The reference document for this statistical plan is the protocol and the accompanying sample data collection documents. Operational aspects related to collection and timing of planned clinical assessments are not repeated in this SAP unless relevant to the planned analysis.

The structure and content of this SAP provide sufficient detail to meet the requirements identified by the Food and Drug Administration (FDA), and International Conference on Harmonization (ICH) of Technical Requirements for Registration of Pharmaceuticals for Human Use: Guidance on Statistical Principles in Clinical Trials¹. All work planned and reported for this SAP will follow internationally accepted guidelines, published by the American Statistical Association² and the Royal Statistical Society³, for statistical practice.

The planned analyses identified in this SAP may be included in clinical study reports (CSRs), regulatory submissions, or future manuscripts. Also, post-hoc exploratory analyses not necessarily identified in this SAP may be performed to further examine study data. Any post-hoc or unplanned, exploratory analysis performed will be clearly identified as such in the final CSR.

The statistical plan described hereafter is an *a priori* plan. It will be approved before any unblinded inferential or descriptive analysis of data pertaining to [REDACTED].

1.1. Rationale for Study

RHA [REDACTED] is an investigational device which was initially assessed for the perioral lines indication in a previous clinical investigation conducted by [REDACTED] and whose premarket approval was approved by the FDA on 22 December 2021.

The purpose of this study is to inject RHA [REDACTED] into the infraorbital regions to achieve volume correction in the infraorbital area and to demonstrate that it is superior to no treatment in subjects aged 22 years and older to support a premarketing authorization application to United States (US) FDA for RHA [REDACTED].

To date, no soft tissue dermal fillers have been approved by the US FDA for use in the infraorbital regions. Therefore, the options for treatment of this area are limited to surgery, injection of one's own fat tissue, or off-label use of the medical devices marketed for different indications. Data about the effectiveness and/or safety are available from retrospective studies and case reports. The majority of the risks from RHA [REDACTED] are expected to be similar to those associated with other hyaluronic acid (HA) dermal fillers used as off-label treatment in the infraorbital. These include risks associated with all skin injection procedures, with the use of anesthetic agents, or with the use of RHA [REDACTED]. In the light of the potential risks and benefits, a prospective clinical study of RHA [REDACTED] HA dermal filler to assess the effectiveness and safety of the RHA [REDACTED] in the infraorbital area is justified.

1.2. Hypothesis

The RHA█ group will be superior to the No-treatment control group for the correction of volume deficiencies in the infraorbital regions as determined by the Teoxane Infraorbital Hollows Scale (TIOHS – 5-point scale from grade 0 to 4) at 12 weeks after the initial treatment or randomization (for the No-treatment control group). An improvement in the TIOHS of ≥ 1 grade compared to pre-treatment for both eyes will be considered clinically meaningful.

Additionally, the change from Baseline in selected questions of the FACE-Q “Appraisal of lower eyelids” domain score (converted to a 0-100 scale – Rasch conversion) at 12 weeks for subjects treated with RHA█ will be statistically superior (by at least 12 points) to the subjects of the No-treatment control group. The average of the raw score for the █ FACE-Q “Appraisal of lower eyelids” will be also improved by 3 points or more for subjects randomized in the RHA█ treatment group at 12 weeks to confirm that the statistical superiority is clinically significant.

2. Study Objectives and Endpoints

2.1. Study Objectives

The study is designed to achieve a series of objectives outlined below.

2.1.1. Primary Effectiveness Objective

To assess the effectiveness of RHA█ (as judged by clinicians and subjects) for the correction of moderate to severe tissue volume deficiencies in the infraorbital regions at 12 weeks after the initial treatment.

2.1.2. Secondary Effectiveness Objectives

To assess the effectiveness of RHA█ for the correction of moderate to severe tissue volume deficiencies in the infraorbital regions up to 52 weeks after initial treatment and 12 weeks after retreatment.

█
█

2.1.4. Safety Objective

- To assess the safety of RHA█ in subjects treated for the correction of moderate to severe tissue volume deficiencies in the infraorbital regions up to 52 weeks after initial treatment and 12 weeks after retreatment

2.2. Study Endpoints

2.2.1. Effectiveness Endpoints

2.2.1.1. Primary Effectiveness Endpoint

The primary effectiveness endpoint of this study is the responder rate after 12 weeks.

The effectiveness of RHA [REDACTED] will be demonstrated if the responder rate for subjects treated with RHA [REDACTED] is statistically superior to the responder rate for subjects of the No-treatment control group 12 weeks (Visit 5) after randomization as assessed by the Blinded Live Evaluator (BLE) using the live-validated TIOHS. [REDACTED]

Additionally, the following 2 conditions must be met:

- The responder rate for RHA [REDACTED] is $\geq 70\%$
- The difference between the responder rate for subjects treated with RHA [REDACTED] and the No-treatment control group is $\geq 50\%$.

A responder will be defined as a subject with a ≥ 1 -grade improvement in both eyes on the TIOHS as assessed by the BLE from before initial treatment and 12 weeks after the initial treatment (Visit 5).

The co-primary endpoint will be the change from Baseline in selected questions of the FACE-Q “Appraisal of lower eyelids” domain score at 12 weeks. The effectiveness of RHA [REDACTED] will be demonstrated if the modified FACE-Q “Appraisal of lower eyelids” change from Baseline score (converted to a 0-100 scale – Rasch conversion) for subjects treated with RHA [REDACTED] is statistically superior (by at least 12 points) to the subjects of the No-treatment control group 12 weeks (Visit 5) after randomization [REDACTED]

Additionally, the following 2 conditions must be met:

- The mean change from Baseline of the modified FACE-Q “Appraisal of lower eyelids” raw score for RHA [REDACTED] is ≥ 3
- The difference between the modified FACE-Q “Appraisal of lower eyelids” change from Baseline for subjects treated with RHA [REDACTED] and the No-treatment control group is ≥ 12 .

[REDACTED] Subjects randomly assigned to the No-treatment control group will receive treatment in Phase 1b, but these data will not be pooled for the primary endpoint analysis.

Superiority will be declared if:

- the lower bound of 2-sided 95% confidence interval for the responder rate for RHA [REDACTED] is at least 70%, and
- the lower bound of 2-sided 95% confidence interval for the difference in the responder rate between subjects treated with RHA [REDACTED] and the No-treatment control group is at least 50%, and
- the lower bound of 2-sided 95% confidence interval for the modified FACE-Q “Appraisal of lower eyelids” raw score for RHA [REDACTED] is at least 3, and
- the lower bound of 2-sided 95% confidence interval for the difference in mean change from Baseline of the modified FACE-Q between RHA [REDACTED] treated group and the No-treatment control group is at least 12.

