6.1.6.2. FACE-Q Scores

For FACE-Q “Appraisal of lower eyelids” domain, the outcome of all the question, described below, will be pooled and data will be transformed so that higher scores reflected superior (positive) outcome and adapted to a scale of 100 units (i.e., worst/lowest score = 0, best/highest score = 100). Transformation of scores will be done according to FACE-Q manual.

The Rasch converted scores will be calculated based on the following domain and questions.

Domain “Appraisal of lower eyelids”:

- a. Excess fat under your eyes?
- b. Excess skin under your eyes?
- c. Puffiness under your eyes?
- d. How noticeable the lines under your eyes are?
- e. Crepey (wrinkled) skin under your eyes?
- f. How old the area under your eyes makes you look?
- g. How tired the area under your eyes makes you look?

Raw score will be derived as follow:

- Not at all: 4
- A little: 3
- Moderately: 2
- Extremely: 1

The converted raw scores for items that make up a scale are added to provide a total score. The total score is converted to a score from 0 to 100. If missing data is less than 50% of the scale’s items, insert the mean of the completed items to calculate the total score and round it to the nearest integer.

[REDACTED]

[REDACTED]

AD-ST-33.06 Effective date: 12-Nov-2020

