8.1. Primary Effectiveness Analysis

Primary endpoint:

Primary endpoint is the responder rate after 12 weeks.

A responder is defined as a subject with an absolute ≥ 1 -grade improvement in both eyes on the TIOHS as assessed by the BLE from before initial treatment to 12 weeks after the initial treatment (Visit 5). A negative change from Baseline value is considered as an improvement. Subject with missing assessment for at least one eye at Visit 5 will be considered as a non-responder.

Responder rate at Visit 5 as assessed by the BLE will be tabulated by treatment group: frequency of responders, percentage of responders along with 95% CI will be tabulated. Fisher's exact test will be performed to compare responder rates between RHA [REDACTED] and the No-treatment control group. Test will be one-sided with a Type I error rate at 0.025. To achieve superiority, the observed P value must be ≤ 0.025 .

[REDACTED]

Missing data will be handled as described in section 6.1.3.1.

Additionally, the following 2 conditions must be met:

- At least 70% of the subjects treated with RHA [REDACTED] must be responders
- The difference between the responder rate for subjects treated with RHA [REDACTED] and the No-treatment control group must be $\geq 50\%$ points.

Co-primary endpoint:

The co-primary endpoint will be the change from Baseline in the modified FACE-Q "Appraisal of lower eyelids" domain score [REDACTED]

[REDACTED] and the average change from Baseline of the modified FACE-Q "Appraisal of lower eyelids" converted raw score at 12 weeks. Missing data will be handled as described in section 6.1.3.1.

[REDACTED]

Superiority will be declared if:

- the lower bound of 2-sided 95% confidence interval for the responder rate for RHA [REDACTED] is at least 70%, and
- the lower bound of 2-sided 95% confidence interval for the difference in the responder rate between subjects treated with RHA [REDACTED] and the No-treatment control group is at least 50%, and
- the lower bound of 2-sided 95% confidence interval for the modified FACE-Q “Appraisal of lower eyelids” raw score for RHA [REDACTED] is at least 3, and
- the lower bound of 2-sided 95% confidence interval for the difference in mean change from Baseline of the modified FACE-Q between RHA [REDACTED] treated group and the No-treatment control group is at least 12.

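### The third superiority bullet bounds the FACE-Q raw score itself at 3, not its change from Baseline, so the 3-point criterion loses its confidence-bound test

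*SAP*

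**What the plan says.** SAP 1.2 states the FACE-Q raw-score criterion as an improvement: the average "will be also improved by 3 points or more for subjects randomized in the" RHA group at 12 weeks. It gives the purpose as "to confirm that the statistical superiority is clinically significant".

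SAP 2.2.1.1 opens the co-primary with "The co-primary endpoint will be the change from Baseline in selected questions of the FACE-Q" lower-eyelid domain. It then sets a condition of at least 3 on a change: "The mean change from Baseline of the modified FACE-Q" raw score in the RHA group. SAP 8.1 also defines the co-primary through a change: "and the average change from Baseline of the modified FACE-Q" converted raw score.

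The decision rule appears twice, in 2.2.1.1 and 8.1, as four lower bounds of 2-sided 95% confidence intervals. The third bullet of each list requires that the modified FACE-Q "raw score for RHA [REDACTED] is at least 3", with no mention of change. The fourth bullet of each list does mention it: "the difference in mean change from Baseline of the modified FACE-Q". The redaction in the third bullet stands where the product suffix is hidden throughout, so it does not account for the missing words.

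On scoring, SAP 6.1.6.2 gives each item 1 to 4, higher being better, and says: "The converted raw scores for items that make up a scale are added to provide a total score".

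**The concern.** The same 3 points are a change in 1.2, in the conditions of 2.2.1.1 and in the co-primary definition of 8.1, but a level in the two lists that decide the trial. A level of 3 on a sum of items scored 1 to 4 is at or near the floor of the scale, so a bound on it says almost nothing about treatment.

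The end of 8.1 makes every superiority criterion, for both the primary and the co-primary endpoint, a condition of overall success. The third bullet is therefore part of the success rule, and it belongs to the criterion meant to show clinical relevance. Two analysts applying the SAP could reach opposite verdicts on the same data, and choosing a reading after the data are seen would undermine a plan that calls itself a priori.

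**Working it through.** The visible SAP gives no figure to reproduce here (no SD, expected change or power for this criterion). The check is what the bullet can and cannot reject.

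**Inputs**
- Item scores 1 to 4, summed (6.1.6.2). A k-item total lies between k and 4k.
- k is not visible. The co-primary uses more than one question (2.2.1.1) from a domain of 7 (6.1.6.2, 8.3.3), so k is 2 to 7.
- RHA arm: 258 subjects (3.3) at 3:1 (3.1) gives 258 × 0.75 = 193.5, taken as 193. A smaller arm of 150 is also used (assumption).
- Item averages of 1.5 and 2 with no change from Baseline (assumptions; the SAP gives none).
- A t interval for the mean (assumption).

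**Formula.** Lower bound = m − t × SD/√n. The multiplier t/√n is 1.972/13.89 = 0.142 for n = 193 and 1.976/12.25 = 0.161 for n = 150. For a given mean m, the SD is largest when all totals sit at k or 4k. Its square is then (m − k)(4k − m) × n/(n − 1), and this gives the lowest bound.

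**Worked case.** k = 4, item average 2, no change, n = 193: m = 8, SD = √(4 × 8 × 193/192) = 5.67, bound = 8 − 0.142 × 5.67 = 7.19.

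**Results under the widest spread (n = 193 / n = 150)**

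| Items k | Lowest possible bound, any data | No change, item average 2 | No change, item average 1.5 |
|---|---|---|---|
| 2 | 1.97 / 1.96 | 3.60 / 3.54 | 2.68 / 2.64 |
| 3 | 2.955 / 2.941 | 5.40 / 5.31 | 4.02 / 3.96 |
| 4 | 3.94 / 3.92 | 7.19 / 7.08 | 5.36 / 5.28 |
| 7 | 6.89 / 6.86 | 12.59 / 12.40 | 9.39 / 9.23 |

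- k of 4 or more: the lowest possible bound already exceeds 3, so the bullet is always met. The values for 5 and 6 items (4.92 / 4.90 and 5.91 / 5.88) fit the same pattern.
- k = 3: data confined to the two extremes fail only when 1 to 3 subjects are off the floor. Any mean of at least 3.18 (n = 193) or 3.23 (n = 150) passes.
- k = 2: any mean of at least 3.36 or 3.41 passes, an item average of about 1.7. Below that it can fail, but it is still a test of the level at Visit 5.

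**Simulation** (4000 trials per setting, n = 193; k = 3, 4, 5 and 7). With no effect and a Baseline item average of 2 or 1.25, the bullet on the level was met in 100% of trials. The same held with a 1-point worsening from an item average of 2. A bound of 3 on the change was met in 0%.

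**What remains of the 3-point criterion.** Only the point-estimate condition tests the change. If the true mean change is exactly 3, the observed mean reaches 3 with probability about 0.50, while a lower 95% bound reaches 3 with probability 0.025. The two rules disagree when the observed mean change lies between 3 and 3 + 0.142 SD (n = 193) or 3 + 0.161 SD (n = 150). For an assumed SD of change of 4, that is 3 to 3.57 or 3 to 3.65.

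**The case against.** The best defence is that the meaning is not really in doubt. Section 1.2, the conditions in 2.2.1.1 and the co-primary definition in 8.1 all speak of a change, and the four bounds match the four conditions one for one. A trial with no improvement could not succeed: the mean change must still reach 3 as a point estimate, and the between-group bound of 12 must still be met. The wording alters the verdict only in the narrow band above. For n = 193, in normal approximation, the chance of landing there exceeds 5% only if the true mean change lies between about 3 − 0.12 SD and 3 + 0.26 SD. The SAP gives no basis for saying that this is likely. The 50% against 2.5% contrast is also general: it concerns one condition at one true value, not the success rate of the trial. Finally, the modified scale probably has fewer than 7 items, since 2.2.1.1 separates selected questions from all questions.

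All of this is fair, and it limits the consequence. It does not remove the error. A pre-specified success rule should not have to be inferred from other sections, and the literal rule is wrong in both places where it stands. A smaller item count does not rescue it either: 4 items are enough to make it vacuous, and 3 nearly so. Reading the raw score as an item average conflicts with the summing in 6.1.6.2, and a 3-point change would then be the whole range from 1 to 4.

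**Conclusion.** The concern holds. Under the summed coding of 6.1.6.2, the third bullet is always met for 4 to 7 items, met except at the floor for 3, and a test of level rather than improvement for 2. The loss is confined to the confidence-bound protection of the within-arm 3-point criterion, which the other three thresholds keep. It matters when the observed mean change falls within 0.14 SD (193 RHA subjects) to 0.16 SD (150) above 3.

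This rests on an item count of 2 to 7, an RHA arm of 150 to 193 and a t interval. The no-change examples also rest on assumed item averages. The result for 4 or more items needs no assumption about the answers, only the 1 to 4 range of each item. Because the error sits in the co-primary success rule, it must be corrected before that rule is applied.

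**What to change.** Reword the third bullet in 2.2.1.1 and 8.1 along these lines: *for the RHA group, the 2-sided 95% confidence interval for the mean change from Baseline to Visit 5 in the modified FACE-Q raw score has a lower limit of 3 or more*.

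Use one score name wherever the 3-point criterion appears. Section 2.2.1.1 says raw score, 8.1 says converted raw score, and 8.3.3 lists the two as separate outputs. The sponsor should confirm that the summed 1 to 4 coding of 6.1.6.2 is meant. The point-estimate condition in 2.2.1.1 is then implied by the bound and may stay.

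The cost is a few words in two bullets, with no extra data or subjects. The criterion becomes stricter than the literal text: the observed mean change must reach 3 + 0.14 SD (n = 193) to 3 + 0.16 SD (n = 150). For an assumed SD of change from 2 to 6, that is 3.28 to 3.85 with 193 subjects, or 3.32 to 3.97 with 150.

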2.2.1.2. Secondary Effectiveness Endpoints

The secondary effectiveness endpoints are:

- Proportion of subjects with both eyes with ≥ 1 -grade improvement on the TIOHS as assessed:
 - By the BLE at each site visit starting from Visit 5 (12 weeks after randomization/ initial treatment) = rate of responders at the given time point

- Proportion of subjects who were “improved” or “much improved” using the Global Aesthetic Improvement Scale (GAIS) as assessed:
 - By the BLE at each site visit starting from Visit 5 (12 weeks after randomization/initial treatment)
[REDACTED]
- Proportion of subjects “satisfied” or “very satisfied” with the effect of the study treatment, using the Subject satisfaction scale as assessed by the subject at each site visit from Visit 3/Visit 3b (4 weeks after initial treatment)
- FACE-Q assessment by the subject through the “Appraisal of lower eyelids” (all questions) scale of the FACE-Q at each site visit starting from Baseline (except for Visit 2)
[REDACTED]
[REDACTED]
[REDACTED]
[REDACTED]
[REDACTED]
[REDACTED]
[REDACTED]

2.2.2. Safety Endpoints

The safety endpoints of this study include the following:

- Adverse events (AEs), with a focus on treatment related AEs based on the TI assessment, and AEs reported from the Common Treatment Response (CTR) diary, from randomization

Post-injection CTR,

Each AE will be coded to a Preferred Term (PT) and associated System Organ Class (SOC) according to an established and validated adverse reaction dictionary (Medical Dictionary for Regulatory Activities [MedDRA], latest available version) before the randomized treatment code is broken.

3. Overall Study Design and Plan

3.1. Overall Design

Enrollment:

This is a multicenter, blinded evaluator, randomized, prospective, no treatment control clinical study to identify whether RHA [REDACTED] is superior to no treatment for the correction of moderate to severe tissue volume deficiencies in the infraorbital regions. The study [REDACTED] [REDACTED] will include at least 20% of subjects with Fitzpatrick skin types IV-VI: including minimum of 10% subjects presenting with Fitzpatrick skin types V or VI of which $\geq 3\%$ will have Fitzpatrick skin type V [REDACTED] and $\geq 3\%$ will have Fitzpatrick skin type VI [REDACTED].

The TI and the BLE will evaluate the subject's infraorbital hollows independently of each other using the TIOHS at Screening (Visit 1) for eligibility. If the assessments of the TI and the BLE are the same or differ exactly by 1 point on the scale, the difference will be considered acceptable. The TI and the BLE must agree that the subject meets the inclusion criterion number 4 (TIOHS grade 2 or 3). Bilateral symmetry is not required. If the subject is eligible, the BLE's assessment will be used for the Baseline of the primary endpoint. If the TI and the BLE do not agree on eligibility, or if their assessments differ by 2 points or more on the scale, the subject will not be eligible.

A black and white image showing a series of horizontal black bars of varying lengths, suggesting a redacted document. The bars are positioned in a descending staircase pattern from top to bottom. The top bar is the longest, followed by a shorter one, then a very long one, then a medium one, then a short one, and finally a very long one at the bottom. The background is white.

Subjects enrolled will be randomly assigned in a ratio of 3:1 at Screening (Visit 1) to receive RHA [REDACTED] or to receive no treatment (No-treatment control group). Subjects receiving RHA [REDACTED] will be further divided by the method of administration (i.e., injection with a needle or a cannula), which will be defined for each site before the beginning of the study. Depending on the site, RHA [REDACTED] will be administered with a 30G ½" needle [REDACTED] or with a 25G 1 ½" cannula [REDACTED]. Site selection will aim to achieve approximately 1:1 distribution between the subgroups. The BLE will be blinded to the study groups (RHA [REDACTED] group or No-treatment control group).

Phase 1a: Up to 12 weeks after the initial treatment for the RHA█ group or after randomization for the No-treatment control group; primary endpoint

Subjects who will be randomly assigned to the RHA [REDACTED] group at Screening [REDACTED] [REDACTED] will receive their injection at Visit 1. The TI or designee will call subjects 72 hours post-treatment (Visit 1 Call). Subjects will come to the site [REDACTED] [REDACTED] 12 weeks (Visit 5, primary endpoint) after the initial treatment. Afterwards, subjects will proceed directly to Phase 2. Phase 1b is not applicable for subjects randomly assigned to the RHA [REDACTED] group.

Subjects randomly assigned to the No-treatment control group at Screening will receive

no treatment in Phase 1a of the study. They will come to the site [REDACTED] [REDACTED] 12 weeks (Visit 5, primary endpoint) after randomization. After completing all assessments for Visit 5, subjects will immediately begin Phase 1b (Visit 1b is on the same day as Visit 5) and will receive their initial treatment with RHA [REDACTED].

[REDACTED]

Phase 1b: after the primary endpoint assessment up to 12 weeks after the initial treatment for the No-treatment control group

Phase 1b is only applicable to subjects initially randomly assigned to the No-treatment control group. Once all evaluations applicable for Visit 5 are completed, subjects will proceed directly to Visit 1b (on the same day). Evaluations completed at Visit 5 will be used for Visit 1b and will become the new Baseline for Phase 1b.

Subjects will receive their initial treatment with RHA [REDACTED] at Visit 1b.

Subjects will follow the same schedule as those initially randomly assigned to the RHA® 1 group: RHA® 1 will be administered on the same day (Visit 1b). The TI or designee will call the subject 72 hours post-treatment (Visit 1b Call). Subjects will come to the site [REDACTED] [REDACTED] 12 weeks (Visit 5b) after their initial treatment. Afterwards, subjects will proceed to Phase 2.

Phase 2 and Exit visit: 12 weeks after the initial treatment up to the end of the study for the RHA [REDACTED] group and the No-treatment control group

Phase 2 will occur 12 weeks after receiving initial treatment with RHA [REDACTED] for subjects in the RHA [REDACTED] and the No-treatment control group (after Phase 1b).

